Study on the Gut Microbial Mechanism of
Negative Symptoms of Schizophrenia

Aug. 25th,2020

1. Subjects

Recruit 30 outpatient/inpatient schizophrenia patients (dominant negative symptoms) in Shanghai Mental Health Center (research group). At the same time, 15 cases of normal healthy people (control group) with similar eating habits and ages in the same region were matched.

Inclusion criteria:

- 1) 18-45 years old, Han nationality, no gender limit;
- 2) Meet the diagnostic criteria of "Schizophrenia" in the American Diagnostic 3) Standards for Mental Disorders (DSM-V);
- 3) The first attack, no antipsychotic drugs have been used in the past six months;
- 4) The PANSS negative symptom subscale has at least 3 items with 4 points and above or at least two items with 5 points and above, and the positive symptoms score is less than 19 points;
- 5) The negative symptom score is at least 6 points or more higher than the positive symptom score;
- 6) The cultural, social and educational background is sufficient to understand informed consent and research content.

Exclusion criteria:

- 1) Combined with DSM-V diagnosis other than schizophrenia;
- 2) G6 \geq 4 points in PANSS, or CDSS \geq 6 points;
- 3) SAS Side Reaction Scale $>$ 3 points;
- 4) Organic diseases of the central nervous system;
- 5) In the past two months, there were people who were dependent or abused on alcohol or other substances, which caused significant impairment of social and cognitive function;
- 6) In the past year, there have been major life events such as widowhood;

- 7) Serious suicide attempts;
- 8) The current patient's severe and unstable physical disease;
- 9) Pregnant and lactating women;
- 10) Have a history of antibiotic use of more than 3 days within 3 months;
- 11) Use probiotics (lactic acid products, etc.) for more than 3 days within 3 months;
- 12) Type 1 diabetes and severe diabetes complications;
- 13) Digestive system diseases such as gastrointestinal inflammation, acute or chronic hepatitis;
- 14) Severe organ diseases, such as cancer, coronary heart disease, myocardial infarction, cerebral hemorrhage;
- 15) Have infectious diseases, such as tuberculosis, AIDS;
- 16) Drug treatment of cholecystitis, peptic ulcer, urinary tract infection, acute nephritis, cystitis or hyperthyroidism.

Withdrawal criteria: Anyone who meets any of the following conditions at any time will terminate the study and complete all the evaluations originally scheduled for the 8th weekend:

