- ① Those who did not meet the requirements of the group were found after joining the group;
- ② The patient or his legal guardian decides to withdraw from the study;
- ③ Serious adverse reactions occur, and the patients cannot tolerate them;
- ④ Serious physical diseases that may endanger the patient's life occur during the study, and the treatment should be terminated regardless of whether it is related to the study medication;
- ⑤ Those who do not use the medicine according to the study protocol, and have a follow-up period of 7 consecutive days or more than 7 days cumulatively;

⑥ Combined use of prohibited drugs or other treatment methods (including ECT, laser, cerebral circulation, brain function, etc.);

⑦ Other circumstances where the main researcher thinks it is necessary to terminate the research;

⑧ Lost to follow-up.

2. Calculation of sample size

Using (G*Power software to calculate, a 20% reduction rate for amisulpride treatment of negative symptoms is taken as the effective response, the first type of error α is 0.05, the second type of error β is 0.2, bilateral Test, the test power $1-\beta$ is 0.8. With reference to the previous literature using amisulpride to treat negative symptoms of schizophrenia, the statistical effect (effect size) is 0.98. This study conservatively estimates that the effect value is 0.8 for sample size calculation. After calculation, The required sample size is 26. According to 10% dropout, about 30 samples from the study group and 15 samples from the healthy control group are matched.

3. Methods

This study included patients with schizophrenia with dominant negative symptoms as the study group; the control group included normal healthy people with similar eating habits and ages in the same region.

1) Drug intervention method of the study group: The study group was given amisulpride tablets first. The initial dose was 50 mg/d. The doctor titrated the dose to the therapeutic amount within 1 to 2 weeks according to the patient's condition. The maximum dose was 300 mg/d, every day. Observe for 8 weeks. Instructions for the patient's use of other drugs: ① It is forbidden to use other antipsychotics, anti-anxiety drugs, other antidepressants or drugs that act on the

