central nervous system (such as nootropics, drugs that improve cerebral circulation or brain metabolism, etc.) during the study and treatment); ② In principle, it is not advisable to combine other medications. For clinical needs (insomnia), non-benzodiazepine sleep aids (such as zopiclone, zolpidem, etc.) can be used first; short-term use of benzodiazepines is allowed , But avoid the use of drugs with long half-life such as clonazepam. Lorazepam or sulrazepam can be used for the purpose of improving sleep (single dose at night before going to bed), and should be stopped in time according to clinical conditions Use; ③ Allow the use of drugs to deal with adverse reactions, symptomatic or physical diseases (no pharmacological conflict with current medications), but the drug dose should be fixed as much as possible during the study period; ④ All combined medications must be recorded in detail.

- 2) Stool collection and processing in the study group: ① Time points for specimen collection: during the baseline period, 2 weeks of treatment, 4 weeks, and 8 weekends. ② Specimen collection method: save 5ml of fresh fecal specimens in the morning, use a dedicated sterile specimen box, collect the specimens under the supervision of a doctor or a trained family member, and immediately notify the designated person by telephone, put the specimens in a sterile EP tube and store them in Minhang Key Laboratory of Shanghai Mental Health Center-80 degree refrigerator. ③ The feces are collected and frozen in two parts. Part of it is reserved for flora analysis, using 16s amplicon sequencing technology to detect fecal DNA to understand the composition of intestinal flora, and the other part is retained.
- 3) Stool collection and processing in the control group: ① Time point of specimen collection: For the real world population, 5ml of fresh fecal specimens were collected at the time of enrollment, 2 weeks, 4 weeks, and 8 weeks after enrollment. ② Specimen collection method:

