- 6) Other items: The two groups monitored Body Mass Index (BMI), abdominal circumference, heart rate, blood pressure, smoking and drinking, and psychoactive substance use before treatment and at the end of 2, 4, and 8 treatment.
- 7) Effectiveness evaluation index: The main evaluation index is the difference between the change of the intestinal microbial flora of the study group and the control group before and after treatment; the secondary evaluation index is the PANSS negative symptom scale score reduction rate $\geq 20\%$ as the effective group, observe the effective group and the ineffective group The difference in the changes of the intestinal microflora of the group; the correlation between the changes of the intestinal microflora of the effective group and immune factors and negative symptoms.

4. Statistical analysis

This experiment used SPSS19.0 software for statistical analysis. The measurement data adopts the mean \pm standard deviation, and the counting data adopts the rate or percentage. One-way analysis of variance was used to compare the two groups at baseline. The comparison of the study group before and after treatment used repeated measures analysis of variance. Changes in negative

symptoms, changes in immune factors and changes in intestinal flora composition were analyzed by PEARSON or SPEARMAN.

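### The main index compares flora change between patients and controls, but no test in Section 4 makes that comparison

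*Combined protocol and SAP*

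**What the plan says.** Section 3, item 7 defines the primary comparison, with change taken over the treatment period: "The main evaluation index is the difference between the change of the intestinal microbial flora of the study group and the control group". Item 3 of the same section gives controls the same four stool samples as patients: "5ml of fresh fecal specimens were collected at the time of enrollment, 2 weeks, 4 weeks, and 8 weeks after enrollment". Item 1 sets the length of treatment: "Observe for 8 weeks".

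Section 4 names the software, the descriptive statistics (mean with SD; rates or percentages) and three inferential methods:

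- Between groups: "One-way analysis of variance was used to compare the two groups at baseline".
- Over time: "The comparison of the study group before and after treatment used repeated measures analysis of variance". The outcome is not named.
- Association: negative-symptom changes, "changes in immune factors and changes in intestinal flora composition were analyzed by PEARSON or SPEARMAN".

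On how the groups relate, Section 1 says only that "15 cases of normal healthy people (control group) with similar eating habits and ages in the same region were matched".

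**The concern.** The main index is a difference between two changes. Testing it needs an analysis that contains both groups and more than one visit. Each group comparison in Section 4 lacks one of these, because the two-group test has no change in it and the longitudinal test has no control group.

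Two things are at stake. First, followed as written, the study reports its main index without a confidence interval or p-value, or an analyst chooses the test after seeing the data. Second, the only longitudinal result on offer is the patients-only ANOVA. If that were applied to flora and read as the answer, a shift common to both groups (season, diet, laboratory batch) could be taken for one specific to patients. The plan does not say it will be read that way, and as a within-patient test it is valid.

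**Working it through.** **1. Stated analyses against the main index**

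| Section 4 method | Both groups? | Change over time? | Tests the main index? |
|---|---|---|---|
| One-way ANOVA | Yes | No, baseline only | No |
| Repeated-measures ANOVA | No, study group only | Yes | No |
| Pearson/Spearman | No group contrast | Yes, as association | No |

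The count is 0 of 3. No test of change between groups appears elsewhere in the document.

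**2. Control samples left unused.** Scheduled: 15 x 4 = 60. After baseline: 15 x 3 = 45. Only the 15 baseline samples fall under a stated two-group test.

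**3. Does the sample-size section supply the missing test?** Inputs from Section 2: effect size 0.8, two-sided alpha 0.05, power 0.80. A 1:1 two-sample t-test needs 25.52, so 26 per group, which reproduces the plan's 26. Allowing for 10% dropout, 26/0.9 = 28.9, against about 30 in the plan. A paired test would need 15 (14.30 rounded up). The 26 thus fits a two-group comparison, but Section 2 names no test, takes its effect size from negative symptoms, and plans only 15 controls. It does not fill the gap.

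**4. Precision and power of the missing contrast.** With complete data and an unstructured covariance, the week-8 difference in change is equivalent to a two-sample t-test on change scores with n1 + n2 − 2 df. In units of the SD of change, SE = √(1/n1 + 1/n2) and the 95% CI half-width is t(0.975) x SE.

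- 30 vs 15: SE = 0.316, df = 43, half-width = 2.017 x 0.316 = 0.638.
- 27 vs 14: SE = 0.329, df = 39, half-width = 2.023 x 0.329 = 0.666.

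The second case assumes that the 10% dropout also applies to controls (15 x 0.9 = 13.5, rounded up).

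Two-sided power at 0.05 (noncentral t, noncentrality d/SE):

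| d assumed for flora change | 30 vs 15 | 27 vs 14 |
|---|---|---|
| 0.5 (assumed) | 0.340 | 0.316 |
| 0.8 (plan's figure for symptoms) | 0.696 | 0.659 |
| 0.98 (plan's literature figure for symptoms) | 0.858 | 0.827 |

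Detectable d at 80% power is 0.906 and 0.946. Rounding controls down (27 vs 13) gives power 0.637 at d = 0.8 and a half-width of 0.683.

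**5. Week-8 contrast or omnibus interaction.** Under compound symmetry with d = 0.8 at week 8, the 3-df group x visit test has power 0.575 / 0.536 (30 vs 15 / 27 vs 14) for a linear profile and 0.728 / 0.687 for a step profile. Which test does better depends on the profile, so one should be named in advance.

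**6. Illustration: the patients-only ANOVA under a shift shared by both groups.** Assumptions: the ANOVA is applied to flora and misread as the main result; n = 27; compound symmetry; SD of change 1, hence residual variance 0.5; true group difference 0. Then F has (3, 78) df and λ = 27 x Σ(m − mean)²/0.5. The linear profile is (0, 0.25d, 0.5d, d) and the step profile (0, d, d, d). At d = 0.5 linear, Σ = 0.1367 and λ = 7.38; step, Σ = 0.1875 and λ = 10.1.

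| Shared shift (SD of change) | Linear | Step |
|---|---|---|
| 0.1 | 0.067 | 0.074 |
| 0.2 | 0.125 | 0.156 |
| 0.3 | 0.235 | 0.314 |
| 0.5 | 0.591 | 0.743 |

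In 20,000 simulated trials per scenario at 27 vs 14, the between-group week-8 test rejected in 4.65% to 5.02%. About 5% is what a valid test gives when the true difference is 0.

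**The case against.** The best counter-argument is about wording. Item 7 reads as awkward translated prose, and its before-and-after-treatment phrase cannot apply literally to untreated controls. It could mean two things: patients against controls, and patients before against after. Section 4's two ANOVAs would fit that reading. But it leaves no purpose for sampling controls at weeks 2, 4 and 8, and even then item 7 and Section 4 would need reconciling. The objection does not remove the gap.

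Other points stand in part:

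- The shared-shift figures measure a possible misreading, not something the plan proposes. They are an illustration, and the finding does not depend on them.
- The power and CI figures presuppose one roughly normal flora score, whereas 16S composition is multivariate and the plan defines no summary measure. They are conditional on that choice.
- Any named between-group test of change would close the gap, including group x time in a repeated-measures ANOVA. The mixed model is a recommendation, not the only remedy.
- Sections 1 and 2 say the controls are matched. No pairs or sets are described, but none are explicitly excluded.

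**Conclusion.** The concern holds and must be fixed. As written, Section 4 contains no inferential analysis of the main index: 0 of 3 methods compare change between groups, and 45 of 60 scheduled control stool samples enter no stated group comparison. The mean and SD would allow a crude descriptive difference, but no interval or p-value. This conclusion rests on the text alone.

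The precision and power figures rest on more: a single flora value per sample, independent groups, the stated numbers completing, and an effect size for flora that the document does not give.

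**What to change.** In Section 4, state one primary analysis:

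- A linear mixed model (SPSS MIXED, REML) on one flora measure, fixed before analysis and giving one value per sample. Which measure to use is a separate point that must be settled first.
- Data from both groups at weeks 0, 2, 4 and 8; fixed effects for group, visit and group x visit; unstructured within-subject covariance.
- Sole primary contrast: study-minus-control difference in change from baseline to week 8, with 95% CI, two-sided 0.05. Week 8 is the end of the planned observation.
- A statement that the 3-df interaction is not primary and that the study-group-only ANOVA is supportive.
- A statement that the groups are analysed as independent, since the text describes similarity in age, region and diet but no pairs or sets. If matched sets do exist, the plan should say so and the model should reflect them.

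The cost is a text change once the flora measure is fixed, with no visits or samples beyond those scheduled. There are two downsides. Power at the planned size is about 70% (30 vs 15) or 66% (27 vs 14) if d = 0.8 is assumed for flora, and runs from 34% to 86% or 32% to 83% over d = 0.5 to 0.98. Also, untreated healthy controls cannot separate a drug effect from illness or setting, so the contrast should be described as a difference in change between patients and controls and no more.

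### The plan fixes no flora quantity, visit or multiplicity rule for its main index or its flora correlations; even one flora summary tested against five correlates carries about a 20–23% chance of a false positive

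*Combined protocol and SAP*

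**What the plan says.** - **Main index (Section 3, item 7).** "The main evaluation index is the difference between the change of the intestinal microbial flora of the study group and the control group". The item frames this as a pre- to post-treatment contrast. No diversity index, distance, taxon, taxonomic level or single visit is attached to it.
- **Secondary indices (same item).** There are two on flora: flora change in patients with at least a 20% PANSS negative reduction against the rest, and the correlation of flora change with immune factors and negative symptoms within that effective group.
- **Assay (Section 3, items 2 and 3).** Stool is analysed "using 16s amplicon sequencing technology to detect fecal DNA to understand the composition of intestinal flora". The number of taxa is not given.
- **Correlates and visits (Section 3, items 2 to 5).** Four cytokines are measured: IL-1β, IL-6, IL-10 and TNF-α. Stool, blood and scales are all taken at baseline and weeks 2, 4 and 8.
- **Analysis (Section 4).** One-way ANOVA compares the groups at baseline, and repeated-measures ANOVA compares the study group before and after treatment. Changes in negative "symptoms, changes in immune factors and changes in intestinal flora composition were analyzed by PEARSON or SPEARMAN".
- **Error rate (Section 2).** The only one given is "the first type of error α is 0.05", in the sample-size calculation. No section gives a correction, a hierarchy or a false-discovery rule.

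**The concern.** A correlation coefficient or a univariate ANOVA needs one number per participant per visit, and a composition does not supply one. It must be reduced to a summary or split into components, and the plan says neither which nor how. The visit for the change is also open, as is the choice between two coefficients.

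Two things are at stake. First, the main index cannot be judged met or not met in advance, because several flora features could each be presented as the primary result. Second, the secondary index multiplies flora quantities by five correlates with nothing controlling the error rate over that family. Some reported links between flora, immune factors and symptoms could then be chance.

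**Working it through.** **1. The plan's own figure.** Section 2 uses two-sided α = 0.05, β = 0.2 and an effect of 0.8, and states: "The required sample size is 26". A two-sample t-test with 1:1 allocation and d = 0.8 needs 26 per group (power 0.807; 25 per group gives 0.791). With 10% dropout, 26/0.9 = 28.9, so 29, which fits the stated figure of about 30. The 26 therefore reproduces as a number per group. It is built on symptom response to amisulpride, so its 0.05 is attached to no flora test.

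**2. Smallest family the plan allows.** One flora summary at one visit against PANSS negative plus four cytokines is 1 × 5 = 5 tests. If independent, the chance of at least one false positive is 1 − 0.95^5 = 0.226.

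**3. If all three changes from baseline are correlated (not stated).** 5 × 3 = 15 tests, and 1 − 0.95^15 = 0.537.

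**4. Allowing for dependence.** Pearson tests were simulated with no true association. The settings were n = 27 (30 patients less 10%), correlation 0.3 among the five correlates, 0.5 between visits, and 0, 0.3 or 0.6 among taxa. There were 1,000 runs for one visit and 600 for three. These correlations and the taxon counts are assumptions, not document figures. Expected false positives are 0.05 × number of tests.

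| Flora quantities | Tests, one visit | Expected false positives, one visit | Chance of ≥1, independent, one visit | Chance of ≥1, simulated, one visit | Chance of ≥1, simulated, three visits |
|---|---|---|---|---|---|
| 1 | 5 | 0.25 | 0.226 | 0.20–0.23 | 0.48–0.49 |
| 5 | 25 | 1.25 | 0.723 | 0.56–0.64 | 0.90–0.97 |
| 10 | 50 | 2.5 | 0.923 | 0.74–0.90 | 0.99–1.00 |
| 20 | 100 | 5 | 0.994 | 0.88–0.99 | 1.00 |
| 50 | 250 | 12.5 | >0.999 | 0.96–1.00 | 1.00 |

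In the first row the correlation among taxa plays no part, so the spread there is simulation error.

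**5. Effective group only.** Section 3, item 7 restricts the correlation to responders, so n will be smaller. At n = 15 the results are similar: 0.20–0.23 for one quantity at one visit, 0.75–0.90 for 10 taxa and 0.96–1.00 for 50.

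**6. After a fix.** One named quantity, visit and test gives a type I error of 0.05. For the five correlations, a per-test threshold of 0.05/5 = 0.01 would hold the family at or below 0.05.

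**The case against.** The strongest reply is that the plan never says flora is tested taxon by taxon, or that correlations are run at each visit. Flora composition could mean one or a few summary indices. The listed weeks are sampling times, and the before-and-after wording of the main index fits a single contrast. Repeated-measures ANOVA can also take all visits in one model. This stands. A reader might infer that false flora findings are close to certain, but the documents do not support that: near-certainty needs a taxon count they do not give. Even with 20 taxa at one visit the chance can be as low as 0.88 when taxa are correlated.

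Three other inferences also go too far:

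- Section 4 does not say that every p below 0.05 is a finding; it states no threshold at all.
- Section 4 does not name the variables for either ANOVA, so it cannot be read as applying them to each taxon.
- The 0.05 in Section 2 is not a promised error rate for flora.

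It is also fair to say that this is a mechanism study of 45 people, and that the arithmetic concerns the secondary correlations.

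None of this supplies the missing definitions. The repeated-measures model covers the study group only, so it settles neither the patient–control contrast nor the correlations. The most favourable reading still leaves five uncorrected tests.

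**Conclusion.** The point holds in this form: no flora quantity, visit or multiplicity rule is fixed for the flora comparisons or for the flora–immune–symptom correlations. For the main index the defect is one of definition, and the documents allow no error rate to be calculated for it. Section 4 also names no test for the patient–control difference in change, which is that index.

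For the correlations, the size depends on choices the plan leaves open:

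- **One summary, one visit:** about 20–23%. This uses only the document's count of five correlates and testing at 0.05.
- **One summary, three visits:** about 48–54%, if each visit is tested.
- **Taxa tested singly at one visit:** about 0.74–0.90 for 10, 0.88–0.99 for 20 and 0.96–1.00 for 50, with assumed taxon counts and correlations.

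The gap should be closed before any flora data are analysed, because it reaches the main index and the choices cannot credibly be made afterwards.

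**What to change.** Amend Section 4, and align item 7 of Section 3 with it:

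1. **One primary.** Name one flora quantity, for example one alpha-diversity index or one overall composition distance, and take its baseline-to-week-8 change. Test it once, patients against controls, at two-sided 0.05 with a named between-group test. A two-sample test on the individual changes would match the index as worded. Which quantity to use is a scientific choice for the sponsor; what matters is that it is fixed.
2. **One change per participant for the correlations.** Use baseline to week 8 in the effective group, with weeks 2 and 4 descriptive.
3. **Multiplicity.** Apply Benjamini-Hochberg at a 5% false-discovery rate within each index to all other flora comparisons and all flora–PANSS and flora–cytokine correlations. Report q-values and label these results exploratory.
4. **Coefficient.** State before the data are seen how Pearson or Spearman will be chosen. Either is acceptable.

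The cost is about a paragraph of text and no new data. Fewer flora associations will be called significant: an isolated association among five tests would need p ≤ 0.05/5 = 0.01, and among 10 taxa × 5 = 50 tests p ≤ 0.001. The fix does not add power. If the flora effect happened to equal the 0.8 used in Section 2 (an assumption, since that value comes from symptoms), 30 patients against 15 controls would give power of about 0.70.
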